Paradata, defined as auxiliary data that capture details about the *process* of interaction with the technology, will drive our understanding of user engagement with the mLab App and of subsequent behavior change. Outcomes from HIV prevention and care studies delivered via a mHealth platform have primarily relied on analyses by group assignment and assume that participants' engagement is equitable within the intervention arm and stable for the duration of the trial. The use of paradata in technology interventions involving HIV prevention and care is an understudied area of interest.⁸⁵ While a number of technology-based HIV interventions have previously suggested that online behavioral interventions are acceptable and efficacious in promoting behavioral change,⁸⁶ a recent review of this literature identified very limited reports of participant engagement, measured through paradata, with a technology-based intervention.⁸⁷ In our own recently published work on the effect of a mHealth app for improving symptom burden in PLWH, we monitored app usage throughout the trial and reported this as part of the final outcomes of our study.⁸⁸ Given our prior work, we will examine paradata since this provides an opportunity to monitor and analyze aspects of the mLab App that may play a role in changes in HIV testing rates and linkage to care. By monitoring and analyzing paradata, components of the mLab App, such as the timing, location, and frequency of the rapid images of HIV tests taken by a user and access to other prevention information, will be instrumental in understanding what components of the intervention mediate behavior change. Engagement with the mLab App will furnish a greater understanding of user satisfaction and retention of our intervention. mLab App paradata will have implications for the scale-up and dissemination of this intervention as well as for the development of future technology-based HIV interventions with targeted behavioral outcomes.

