Scientific Premise. YMSM and YTGW currently face barriers to HIV testing in clinics (e.g., socioeconomic

Overview of Study Aims, Design and Methods. Table 1 presents an overview of the design, participants, and data analysis plan for each aim.

Scientific Rigor. We will use a careful iterative process to refine the usability and test the efficacy of the mLab App for increasing the uptake of rapid home HIV self-testing. To increase scientific rigor we will: 1) have an image of the participants’ OraQuick test result ensuring the validity of self-reported testing collected via

surveys; 2) use validated measures; 3) use a randomized design to reduce bias in study arm assignment; 4) exercise extensive retention efforts to achieve high retention and reduce selection bias; 5) publish our design and analysis plan on clinicaltrials.gov before we commence data collection; 6) publish anonymized public use data sets after primary analyses are reported. Consideration of sex as a biological variable. We do not aim to

Table 1. Overview of Design, Methods, Participants, and Data Analysis

Aim	Design/Methods	Participants	Data Analysis
1	Usability Evaluation	Heuristic evaluation: human-computer interaction experts (N=5); End-User testing: YMSM and YTGW (N=20); Youth Advisory Board (N=10)	Quantitative and qualitative summary of heuristic violations; thematic analysis of think-aloud protocol, quantitative summary of mouse clicks, time, etc.
2	Randomized controlled design	High-risk YMSM and YTGW (N=525; arm 1 n=210, arm 2 n=210, arm 3 n=105)	Descriptive statistics; Linear regression model
3	Analysis of Para Data	Data Collected through Participant use of the mLab App (N=210)	

evaluate sex differences; the justification for only including assignment of male sex at birth is that the epidemiologic data demonstrate a clear, disproportionate impact of HIV on young racial and ethnic minority men.

Aim 1: Refine the mLab App – a mobile and connected health intervention for increasing the uptake of rapid home HIV self-testing and linkage to care – by employing rapid cycle iterative design methods with feedback from human computer interaction experts (N=5), end-users (N=20), and youth advisory board members (N=10). There are three steps with refinements to the mLab App following each step. Step 1.

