Design Overview. A randomized controlled trial will be conducted with 525 young men over 12 months. Participants will be randomly assigned to the mLab App arm 1 (intervention) or a control arm 2 (standard of care HIV testing information arm) or arm 3 (OraQuick HIV home tests).¹²⁷ Participants in arm 1 will receive access to the mLab app and HIV home test kits, those in arm 2 will receive standard of care HIV information only. The primary comparison will be between arms 1 and 2. Participants in arm 3 will receive HIV home tests kits, but not access to the mLab app. Participants in all arms will receive standard preventive care at baseline. **Recruitment.** Our recruitment activities will mirror those described in Aim 1. Step 2. We will recruit youth from both Chicago and NYC as well as the entire state of Illinois and neighboring states of Wisconsin,

Michigan and Indiana in the Midwest; and all of the state of New York and neighboring states of Connecticut and New Jersey. We will recruit on Grindr and other social media using banner or pop-up ads that target YMSM and YTGW from these areas.

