Study Enrollment. Study participants will come in to our study site in NYC or Chicago to provide informed consent, enroll, and complete a self-administered baseline survey on an iPad. Prior to enrollment into the RCT participants will be consented to screen and administered a rapid HIV test to determine eligibility. If a participant is found to be preliminary positive in the screening procedures they will be linked to care at NYP in New York or Lurie Children's Hospital in Chicago or a healthcare provider of their choice. If they are non-reactive they will be randomized and enrolled into the trial. The baseline survey will include questions on demographic characteristics; health literacy¹³¹; sexual risk behaviors including number of men (and women) they engaged in anal or oral sex with, condomless anal intercourse, as well as their HIV testing history and opinions regarding HIV testing. The baseline survey will also include questions on PEP/PrEP use and adherence, drug and alcohol use,¹³² and the HIV Risk Index.¹³³ After completing the baseline survey, study participants in all three study arms will receive condoms, an information sheet on HIV prevention, PrEP assessment, referral information for clinics that provide PrEP, and a card with the study team's contact information and the NYP/Columbia Comprehensive Care Clinic Phone/Text Number (NYC) and Northwestern/Lurie Children's Hospital (Chicago).

Randomization. After providing informed consent, youth will be randomized to study arms in a 2:2:1 ratio of : arm 1-mLab App (2), arm 2-Standard of Care HIV information arm (2), arm 3-HIV home tests (1). We will use

stratified randomization¹³⁴ to ensure equal representation between treatment groups at each study site (Chicago vs. NYC).¹³⁵ To reduce opportunities for selection bias, we will use a variable permuted randomization block design¹³⁶ where the block size itself is randomly selected (i.e., blocks of five to ten). The advantage of the permuted block design is that treatment assignment is pre-determined before the trial begins and then assignment remains static throughout the course of the trial.¹³⁷ Within each city stratum, a computer program will randomly assign each participant to the next treatment allocation from a random-permuted block randomized sequence. All **three arms** will receive standard-of-care HIV/STI testing-related risk reduction counseling, a box of condoms, PrEP assessment, and referral information for clinics that provide PrEP.

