Missing Data. Multiple imputation (MI) methods will be applied to address missing values under the missing at random (MAR) assumption (i.e., missingness can be fully accounted for by variables with complete information).¹⁴¹ These analyses will be complemented with assessment of how sensitive the inferences are to the MAR assumptions. Sensitivity analysis will be performed based on selection models for dropout.¹⁴²⁻¹⁴⁴ Intention-to-Treat (ITT) Analysis: All analyses will use the ITT principle,¹⁴⁵ which requires subjects' data to be analyzed as randomized, regardless of whether they used the mLab App or not.

Aim 3: Monitor and analyze paradata to understand the effect of user engagement of the mLab App on improving HIV testing rates and linkage to care.

To understand barriers and/or facilitators of its use, the mLab app will automatically collect paradata for each user interaction throughout the study. This paradata is considered "free" in that it does not require any additional effort from the user.¹⁴⁶ This data will be analyzed for each user, as well as aggregated to understand what component of the intervention lead to behavior change. We will specifically examine who uses the mLab App and how frequently it is used over time.

Methods. We will capitalize on the use of the extant mLab software which is written as a mobile-friendly web application in hypertext markup language (HTML), hypertext preprocessor (PHP), JavaScript, and Python (for computer vision), and integrates with REDCap for backend data storage. On each page of the mLab app, a PHP script logs every user interaction before the page of the application is displayed to the user. Therefore, any event that would refresh or send the user to a new page (e.g., HTML links) initiates an event-driven paradata capture. The PHP script transmits the data to REDCap through the secure REDCap API.

Data Analysis. The primary paradata that will be collected is shown in Table 4. From this data, we will derive the following use data for each session: duration on each page, page progression through the application, time from login to result, number of rapid test pictures previewed before sent for result, and total time prior to logout. We will analyze the data on multiple scales and perspectives: individual-level (i.e. user-level), application-level, page-level, session-level, and how these differ by demographic characteristics, HIV testing history, technology

Table. Paradata Collected for Each mLab Event

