We will analyze difference in the aggregated data by demographic group (age, race, and risk level) to allow us to better understand engagement with the intervention and potential facilitators and barriers to mLab App use. We will evaluate if grouping by HIV status affects these results in any way (e.g., do HIV+ users engage with features differently than HIV- users?). Finally, as a web application, there is potential for slightly varied experiences on different devices or web browsers, and we will evaluate if there are differences in mLab paradata across devices and browsers.

Risks, Benefits & Monitoring

Potential Risks

The risks of participating in this study are:

We will discuss each of these risks below and describe the protection against these risks under “Adequacy of Protection Against Risks.”

General Risks:

1. A risk of taking part in this study is the possibility of a loss of confidentiality or privacy, including that associated with the app on the participants' phone. Loss of privacy means having their personal information shared with individuals outside of the study team who were not supposed to see or know about their information. The study team plans to protect the privacy of participants. Their plans for keeping your information private are described in the Privacy section of Protection Against Risk.

Risks Specific to the Use of OraQuick:

1. **Subjects must follow package instructions on the OraQuick test and always read the test results from the OraQuick test themselves given that the accuracy of the mLab application has not been proven.** Confirmatory HIV testing is still needed.
2. Participants may mistakenly believe that a negative result of the OraQuick Test means that they are not infected with HIV. There is a chance that the test does not detect an HIV infection. To offset this risk, participants will be repeatedly told that a negative result in the OraQuick test does not mean that they are not HIV infected, since infections that occurred within the prior three months may not be detected by the test, and that condoms should still be worn to avoid the risk of HIV and other STIs.

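### Aim 3 sets a causal goal for app engagement but plans only mostly descriptive comparisons of self-selected use in arm 1, so motivation to test can pass for an engagement effect

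*Combined protocol and SAP*

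**What the plan says.** The aim is worded causally: "Monitor and analyze paradata to understand the effect of user engagement of the mLab App on improving HIV testing rates and linkage to care". The Aim 3 text adds that paradata will be "aggregated to understand what component of the intervention lead to behavior change". The Background paragraph on paradata says that use of app components "will be instrumental in understanding what components of the intervention mediate behavior change", and that the findings bear on scale-up and on the design of later interventions.

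The data come from one arm. Table 1 gives the Aim 3 source as "Data Collected through Participant use of the mLab App (N=210"), which is the size of arm 1. The Aim 2 Design Overview confirms that no other home-test arm can supply paradata: "Participants in arm 3 will receive HIV home tests kits, but not access to the mLab app".

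The Aim 3 Data Analysis section examines use at user, application, page and session level, and "how these differ by demographic characteristics, HIV testing history, technology" use and outcome measures. It also breaks use down by age, race, risk level, HIV status, device and browser, and adds heatmaps and image-quality work. The longitudinal analysis it mentions asks whether user experience changes with repeated use.

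Two statements elsewhere matter. The Aim 1 justification of eligibility criteria promises control for PrEP use at follow-up in every analysis. The Aim 2 Study Enrollment section says that the baseline survey covers health literacy, an HIV Risk Index and sexual risk behaviours "as well as their HIV testing history and opinions regarding HIV testing".

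**The concern.** Engagement is not randomised. A participant who already meant to test has reason to open the app, read its content and test, whether or not the app changed anything. Comparing use with outcomes inside arm 1 then mixes any effect of engagement with differences between the people who engaged.

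The plan gives the reader no means of separating the two. The baseline measures closest to inclination to test are collected but not assigned as covariates for Aim 3. Nothing requires that the engagement being analysed happened before the testing it is meant to explain.

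At stake is the use to which Aim 3 is put. If a component is credited because motivated users favoured it, the scale-up and design decisions that the Background anticipates would rest on who used the app, not on what it did. The randomised primary comparison does not depend on Aim 3.

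**Working it through.** **The plan's own figure.** There is none for Aim 3: no power, effect size or estimator. The only power statement is for Hypothesis 1 (at least 80%). With 210 × 0.8 = 168 per arm and 40% vs 60% testing, a two-sided 0.05 test has 95.9% power, so that bound is met. It says nothing about Aim 3.

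**Does any stated control cover prior inclination to test?**
- Testing history and risk level are factors by which *use* is compared. That shows who uses the app; it does not adjust an engagement-testing association.
- PrEP use at follow-up is measured after randomisation, so it is not prior motivation. The protocol itself notes that PrEP guidelines include 3-monthly testing, which ties the variable to the outcome.
- Entry excludes people tested in the past 6 months and current PrEP users. This narrows variation in motivation but does not remove it.
- The arm 1 vs arm 3 contrast informs the app as a whole, not engagement or components.

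**Illustration 1: two kinds of user, true engagement effect zero.** From the documents: 60% testing in arm 1. Assumed: half of arm 1 is motivated; 75% of motivated and 45% of other users test (overall 0.5 × 0.75 + 0.5 × 0.45 = 0.60); 70% and 30% respectively are high engagers.
- High engagers: (0.5 × 0.7 × 0.75 + 0.5 × 0.3 × 0.45) / 0.5 = 0.66
- Low engagers: (0.5 × 0.3 × 0.75 + 0.5 × 0.7 × 0.45) / 0.5 = 0.54
- Spurious gap: 12 points. Odds ratio (0.66/0.34) / (0.54/0.46) = 1.65.

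With weaker assumed links (70% vs 50% testing, 65% vs 35% high engagers), the rates are 0.63 and 0.57: 6 points, odds ratio 1.28. With equal high and low groups and a two-sided 0.05 test, the first gap would be significant in about 35% of trials (N=168) to 43% (N=210), the second in about 12% to 14%.

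**Illustration 2: graded motivation, true engagement effect zero.** Assumed: motivation M is standard normal; logit P(high engagement) = a + b·M and logit P(test) = c + b·M. The intercepts are set so that 50% are high engagers and 60% test, and engagement and testing are independent given M. Gaps are from unrounded rates.

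| Odds ratio per SD of M (both links) | Testing, high vs low engagers | Gap, points | Crude odds ratio | Significant at 0.05, N=168 to 210 |
|---|---|---|---|---|
| 1.0 | 60.0% vs 60.0% | 0 | 1.00 | 5% |
| 1.5 | 61.8% vs 58.2% | 3.7 | 1.16 | 7% to 8% |
| 2.0 | 64.7% vs 55.3% | 9.5 | 1.48 | 24% to 29% |
| 3.0 | 69.5% vs 50.5% | 19.1 | 2.24 | 72% to 81% |

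**How much would adjustment help?** Logistic regression of testing on engagement, N=210, 2,000 simulated trials per cell, adjusting for a baseline proxy with an assumed correlation with M. Entries are the share of trials with a significant engagement coefficient although the true effect is zero.

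| Odds ratio per SD | Unadjusted | Correlation 0.5 | 0.8 | 1.0 |
|---|---|---|---|---|
| 2.0 | 26% | 19% | 8% | 4% |
| 3.0 | 81% | 58% | 20% | 5% |

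Adjustment reduces the problem; only a perfect measure of motivation removes it.

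**The case against.** The strongest reply is that Aim 3 is largely usability work: who uses the app, for how long, where they seek help, how good the images are. It has no hypothesis and no power claim, and it does not feed the primary analysis. The comparison with outcomes is one item in a list. On that view a change of wording is enough. This largely stands: the defect is causal wording over a descriptive analysis, and relabelling is the first part of the remedy. It does not dispose of the point, because outcome measures are among the comparison factors and the Background ties the findings to scale-up.

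A reader might infer more than the documents support:
- *That Aim 3 estimates an engagement effect.* No estimator is specified.
- *That factors are examined one at a time.* The text lists factors without saying whether they are taken singly or jointly.
- *That prior motivation is ignored altogether.* Testing history, risk level and the entry criteria all touch it, though none is an adjustment.
- *That engagement will look effective.* It can. Weak links move the false-positive rate only from 5% to 7–8%, and in both two-group examples most trials would show no significant result. Direction is not assured for every metric either: the plan reads help-page visits as a sign that something was unclear.

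Adjustment is also no cure. The survey items are in an attachment not seen here, so how well they capture motivation is unknown.

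**Conclusion.** The point holds as a mismatch between goal and analysis. Aim 3 asks causal questions about engagement and components, and the plan offers only comparisons of self-selected use in one arm, with no adjustment for baseline inclination to test and no time ordering. A spurious association is possible, most plausibly upward. Its size cannot be fixed from the documents: 0 to about 19 points, over assumed motivation odds ratios of 1 to 3 per SD on both engagement and testing, an even engagement split and 60% testing. Only the 60% and the N come from the plan. The matter should be corrected before Aim 3 is analysed; it does not threaten the Aim 2 result.

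**What to change.** 1. **Label.** Call Aim 3 exploratory and associational. Drop *effect*, *lead to* and *mediate* for engagement and components. The randomised arm 1 vs arm 3 contrast can be cited for the app as a whole, but it does not identify mediation.
2. **Engagement measure.** Use time-stamped events that are not part of a test session and that precede the outcome window: for example, months 0–6 prevention pages, messages, help and logins not tied to a test, related to testing in months 7–12. This also prevents a self-test done in the app from counting as both engagement and outcome.
3. **Model.** Pre-specify one arm 1 regression adjusted for baseline testing history, testing opinions, HIV Risk Index, health literacy, age and site.
4. **Sensitivity analysis.** Repeat it with months 0–6 testing as a further covariate. Early testing may prompt later app use and also predict re-testing. It may equally lie on the path from engagement to re-testing, hence its place here and not in the main model.
5. **Other outcomes.** Report first-6-month testing and linkage to care descriptively.
6. **Limitation.** State that residual confounding remains after adjustment.

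The cost is analysis-plan wording, one extra regression and its sensitivity run, on data already to be collected. The time-ordered model uses neither months 7–12 engagement nor the first-6-month outcome.

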1. Unique Code
2. Page accessed
3. Time stamp
4. Rapid test image
5. Internet browser type
6. Operating system
7. Device

use, and outcomes measures. At the app-level, we will analyze timestamp data including time of day and day of the week that HIV self-testing is performed. We will also analyze the time-to-HIV self-testing result from App login -- a primary indicator of usability. Efficiency is a major construct of the Health-ITUDEM model, the guiding theoretical framework for our study (see Figure 4). Additionally, we will measure the amount in bytes of user data transmitted. Importantly, longitudinal analysis will determine if user-experience changes with repeated use.

The paradata collected from each page will be analyzed to generate a “heatmap” of user-interaction (i.e., the distribution of activity for each link/button). Use of the heatmap will inform user duration on each page of the application user interaction with the HIV prevention content, the contact pages, and the help page. We will explore usability issues with consideration for how many times users accessed help, and what page of the mLab app referred them to the help, implying the need for clarification. Similarly, contact page paradata will be analyzed to determine at what point in the use of the imaging software (the mLab) users initiated contact with the study team and/or the clinic. Specifically, referring pages to the contact page will be analyzed (i.e., do users engage with contact resources only after a diagnosis is provided?). Finally, we will use paradata to understand when users disengage with the mLab app (e.g., logout after received diagnosis, logout prior to diagnosis, session timeout).

Since the mLab App provides an image-based diagnosis of HIV rapid tests, paradata will be used to understand the process of capturing a photograph for analysis. To this end, we will count the number of images previewed prior to submission of a final image for mLab analysis. Within each image, we will perform digital image analysis to determine orientation, luminosity, and major colors within an image – all factors that would indicate successful analysis in mLab. Importantly, this analysis will be used to improve the computer vision algorithm.

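### Aim 3 relates app engagement to HIV testing through measures, such as test-image counts, that are themselves records of a test

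*Combined protocol and SAP*

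**What the plan says.** Aim 3 is worded as a question about an effect: "Monitor and analyze paradata to understand the effect of user engagement of the mLab App on improving HIV testing rates and linkage to care". Its opening paragraph adds that the data will be "aggregated to understand what component of the intervention lead to behavior change", and that "We will specifically examine who uses the mLab App and how frequently it is used over time".

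The Background paragraph on paradata lists the components of interest as the "timing, location, and frequency of the rapid images of HIV tests taken by a user and access to other prevention information", and says these "will be instrumental in understanding what components of the intervention mediate behavior change".

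The table of paradata items under Aim 3 includes "Rapid test image". The use measures derived for each session include "time from login to result, number of rapid test pictures previewed before sent for result". The Data Analysis text of Aim 3 says use will be examined for differences by, among other things, the outcome measures.

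The primary outcome of Aim 2 is self-reported HIV testing over the preceding six months, asked at 6 and 12 months. The same section says the photograph of the OraQuick test will be used to confirm that self-report in arm 1. Under Reminder notifications, arm 1 is told to use the app and the kit together at months 3, 6, 9 and 12.

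**The concern.** One photograph serves on both sides of the comparison: it counts as engagement and it verifies the outcome. A user who tests through the app necessarily produces a session, an image and page loads. A user who does not test produces none of these for testing. Relating such measures to testing in the same period therefore returns a positive association whether or not the app changed anyone's behaviour.

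The text does not separate testing events from other use, does not require engagement to come before the test, and states no model or adjustment for this analysis. Paradata come from arm 1 alone, so randomisation gives no protection here. The Background says the paradata results have implications for scale-up and dissemination. An association produced by the definition of the measure could lead the team to credit the wrong app features.

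**Working it through.** **The plan's own figure.** Aim 3 states none. The nearest is power of at least 80% for Hypothesis 1. With 210 × 0.8 = 168 per arm and 40% against 60%, power is 95.9% per comparison, and 0.959² = 92.0% for both if independent. The statement holds as a lower bound, and nothing below depends on it.

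**Inputs from the documents.** Arm 1 has 210 participants (Table 1). Attrition is 20%, six-month testing in arm 1 is 60%, and alpha is 0.05 two-sided (sample size section). Two kits are supplied for the first six months (Arm 1 description). This gives 168 users, 60% of them tested.

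**Assumptions, because the documents give no figures.** A share q of testers test through the app (0.25 to 1), and 40% of those do so twice. Non-test sessions average 1, 4 or 8 per user and are independent of testing. Their spread is either Poisson or much wider (gamma-Poisson, shape 1).

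**Step 1: image-based measures.** If self-report is accurate, P(tested | image) = 1. Without an image, P(tested | no image) = 0.6(1 − q)/(1 − 0.6q):

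- q = 0.25: 0.45/0.85 = 53%, a gap of 47 points
- q = 0.5: 0.30/0.70 = 43%, a gap of 57 points
- q = 0.8: 0.12/0.52 = 23%, a gap of 77 points

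These gaps arise with no engagement effect at all.

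**Step 2: total sessions.** I simulated 1,000 data sets per setting with no true effect and fitted a logistic regression of tested (yes/no) on total sessions. Cells show the median odds ratio per session and the percentage of data sets with p < 0.05.

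| Non-test sessions | q = 0.25 | q = 0.5 | q = 0.8 | q = 1 |
|---|---|---|---|---|
| Poisson, mean 1 | 1.34, 49% | 1.74, 97% | 2.54, 100% | 3.91, 100% |
| Poisson, mean 4 | 1.08, 17% | 1.18, 55% | 1.31, 93% | 1.42, 99% |
| Poisson, mean 8 | 1.04, 11% | 1.09, 33% | 1.15, 66% | 1.20, 86% |
| Wide spread, mean 1 | 1.18, 29% | 1.41, 81% | 1.83, 99% | 2.42, 100% |
| Wide spread, mean 4 | 1.02, 7% | 1.04, 16% | 1.06, 32% | 1.08, 49% |
| Wide spread, mean 8 | 1.01, 6% | 1.01, 8% | 1.02, 12% | 1.02, 15% |

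**Step 3: test sessions removed.** The same regression on non-test sessions only gives median odds ratios of 0.99 to 1.01 and 3% to 6% significant in all 24 settings. Simulation error near 5% is about 0.7 points.

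**The case against.** The strongest reply is that the plan never specifies a regression of testing on sessions. Most of Aim 3 is usability work: page heatmaps, help and contact referrals, point of disengagement, image quality, and device and browser differences. Time from login to result and the number of pictures previewed are sound measures for that purpose, and the plan calls the former a main indicator of usability. The list of components also includes access to prevention information, and Aim 3 names prevention, contact and help pages, so measures that are not tests already exist. Aim 3 carries no formal hypothesis.

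Most of this stands, and it limits the point to one analysis. It does not remove the point. The effect of engagement on testing is a numbered aim, image frequency is named among the components said to show mediation, and use is to be compared by outcome measures. Following that text gives a circular result, not merely an unspecified one.

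A reader might go further and infer that any engagement measure is almost certain to appear to raise testing. The documents do not support that. They give no session counts and no share of tests done in the app, and participants may continue to test elsewhere. A false-positive rate of 99%, as at a Poisson mean of 4 with every tester using the app, is close to the worst case. Under heavy and variable non-test use the excess nearly vanishes.

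**Conclusion.** The concern holds for the engagement-to-testing analysis in Aim 3.

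- **Image- and result-based measures:** the bias is definitional. The gap is 47 to 77 points for q between 0.25 and 0.8, given accurate self-report and the planned 60% testing rate.
- **Total sessions or frequency of use:** the direction is clear and the size is unknown. False-positive rates run from about 5-6% to about 100%, depending on quantities the documents do not give.
- **Content, help and contact pages:** these are not tests, but they can be inflated if opened while the user is logged in to test.

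The usability analyses and the randomised Hypothesis 1 comparison are unaffected. This is a cheap improvement to one analysis and does not threaten the trial's main result.

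**What to change.** For the engagement-to-testing analysis only:

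1. Define engagement from non-test content: prevention information, messages, services, contact and help pages. Exclude test, image, result and test-history pages. Exclude or flag other pages opened during a test session.
2. Relate engagement in months 0-6 to re-testing in months 7-12, adjusting for baseline testing history and for testing in months 0-6.
3. Report an association within arm 1, not an effect or mediation.

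A finer split, months 0-3 against months 4-6, is tempting but should not be used. As described, the outcome is a survey item covering six months and cannot be divided that way. Dating tests from the app instead would drop tests done elsewhere. The cut would also fall on the scheduled 3-month test and its reminders. The month-6 boundary coincides with a scheduled test too, but there it matches the survey windows and Hypothesis 1b, and test pages no longer count as engagement.

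Page and time stamp are already logged for each event, and the 12-month survey already supplies the outcome, so no new data are needed. The cost is that testing in the first six months becomes a covariate and is not an outcome in this analysis. Confounding by motivation to test remains and should be stated.
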